To compare the performance, as measured by the stone clearance rate at time of percutaneous nephrolithotomy, of the ShockPulse-SE Lithotripsy System to the Trilogy Lithotrite.

Study Endpoints

Primary Endpoint

Stone clearance rate defined as the kidney stone surface area measured by preoperative computed tomography (CT) scan divided by the time to remove the targeted stone burden.

Time to remove the targeted stone burden is measured at time the lithotripter unit starts fragmenting the stone to time all fragments are removed from the kidney based on visual inspection. This is prior to final visual inspection of the kidney with a flexible nephroscope.

Additional Endpoints

1. Device malfunctions
2. All complications measured by the Clavien Classification of Surgical Complications

Stone free status as defined by the presence or absence of stone material on postoperative day 1 CT imaging

This study is a post-market, prospective, randomized, multicenter, 2-arm, comparative trial.

Scale and Duration

A total of 100 subjects will be enrolled and treated at 3 study sites across the USA. Each subject will be followed for approximately 6-12 weeks after the study procedure. It is anticipated for the entire study to last approximately 12 months.

***All sites will perform 10 independent PCNL cases, outside of the study period, using the Trilogy lithotrite to become accustomed with the device prior to enrolling patients.**

Treatment Assignment

The patients will be block randomized 1:1 to either stone removal with the Trilogy or the ShockPulse–SE device. All randomization will occur at the central study site via computer randomization by the statistician to limit selection bias.

Justification for the Study Design

This study will compare performance of two devices for the treatment of large renal calculi. The study has been designed as a prospective, multi-centric, randomized, comparative study. The intent of this design is to minimize bias and to allow for statistical comparison of the two treatment groups.

Subject Selection

Study Population and Eligibility

Patients who meet all of the inclusion criteria and none of the exclusion criteria will be considered for inclusion in the study.

Inclusion Criteria

1. ≥ 18 years of age
2. Stone burden ≥ 1.5 cm as measured on preoperative CT scan
3. Patient is scheduled to undergo a percutaneous nephrolithotomy procedure
4. Willing and able to provide informed consent

Exclusion Criteria

1. Pregnant

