The primary outcome, clearance rate, will be calculated by dividing the stone surface area by the clearance time. To compare the clearance rate between groups a mixed effects model will be used including treatment group as a fixed effect and site (hospital) as a random effect. Any demographics that were found to be unbalanced between groups may also be included in the model as covariates.

Device malfunctions will be recorded and summarized by treatment group. The proportion of cases experiencing device malfunctions will be compared between groups using Fisher's Exact test. All subject complications will be recorded and summarized using the Clavien Classification of Surgical Complications. The proportions of subjects experiencing complications will also be compared between groups using Fisher's Exact test. The number (and percent) of patients found to be stone free at 6-12 weeks post-op will be summarized and compared between groups using Fisher's Exact test.

The main analysis of the primary endpoint will be performed on the ITT dataset. Supportive analyses may be performed on the PP dataset. All reporting and analysis of adverse events and complications will be done using the SA data set.

Control of Systematic Error/Bias

To minimize selection bias there will be a single randomization schedule managed at the lead investigative site. Upon subject enrollment, all participating sites will contact the main site for experimental group randomization. The randomization will be a permuted block randomization that will help ensure a reasonable balance of group assignment throughout the study enrollment period.

Number of Subjects per Investigative Site

The maximum number of subjects for any single site is 85.

Data Management

Data Collection, Processing, and Review

Subject data will be recorded in a limited access, secure, web-based electronic data capture (EDC) system called REDCap. REDCap is designed to comply with HIPAA regulations. REDCap is not 21 CFR Part 11 compliant; however, this data will not be submitted to the FDA as it is part of a post-market study comparing two commercialized devices for their cleared intended uses.

The conduct of clinical studies pertaining to the use of electronic records and signatures. Database backups are performed regularly.

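### Allocation uses one schedule for three sites with no stated stratification by site, so devices can be unevenly split within a site by chance; this costs a little precision and does not cause bias

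*Combined protocol and SAP*

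**What the plan says.** Treatment Assignment gives the ratio: "The patients will be block randomized 1:1 to either stone removal with the Trilogy or the ShockPulse–SE device". Control of Systematic Error/Bias gives the mechanism: "To minimize selection bias there will be a single randomization schedule managed at the lead investigative site". Sites telephone or write in for each assignment ("Upon subject enrollment, all participating sites will contact the main site for experimental group randomization"), and the stated aim of the blocks is balance over time: "The randomization will be a permuted block randomization that will help ensure a reasonable balance of group assignment throughout the study enrollment period". Block size is not given. Neither site nor any other factor is named for stratification in the synopsis, Treatment Assignment, the screening visit or the bias section. That allocation is unstratified is therefore an inference from this silence and from the word single, but it is the natural reading.

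On size, Scale and Duration says "A total of 100 subjects will be enrolled and treated at 3 study sites across the USA", and the section on subjects per site adds "The maximum number of subjects for any single site is 85".

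On analysis, Statistical Methods says that for clearance rate "a mixed effects model will be used including treatment group as a fixed effect and site (hospital) as a random effect". The synopsis names only a t-test, which has no site term. Device malfunctions, complications and stone-free status are compared by Fisher's exact test, also without site.

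**The concern.** The plan treats site as a source of variation when it analyses the primary endpoint, but not when it allocates patients. The clearance clock is started and stopped by the operating investigator, and each site must complete ten Trilogy cases before enrolling, so it is reasonable to expect some difference between hospitals. If one hospital happens to use one device more often, part of the difference between hospitals enters the observed device difference in that trial. A site term removes most of this; an analysis without one does not. At stake is some precision in the primary comparison, and more in any comparison that ignores site.

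**Working it through.** **The plan's own figure.** Two-sided t-test, alpha 0.05, power 90%, effect size 0.7: the noncentral t calculation gives 43.87, so 44 per group, with power 90.1%. The stated 44 is reproduced, and stratifying by site would not change it.

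**Inputs.** From the documents: 100 patients, 50 per arm, 3 sites, cap of 85 per site. Assumed, because the documents do not give them: site sizes (34/33/33 to 85/8/7), blocks of 4, patients from the sites arriving in random order, and the between-site share of variance (ICC) of 5%, 10% or 20%.

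**How uneven a site can become.** Let d_k be the difference between arms at site k, which has n_k patients. Under one shared schedule with random arrival, E[d_k²] = n_k(N − n_k)/(N − 1), whatever the block size.
- 34/33/33: (34×66 + 33×67 + 33×67)/99 = 6666/99 = 67.3 summed over sites.
- 85/8/7: (85×15 + 8×92 + 7×93)/99 = 2662/99 = 26.9.

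In simulation at equal sites, some site is out of balance by 6 or more patients in 46% of trials and by 8 or more in 24%. The mean difference at a site is 3.8 patients, against about 1 with site-specific blocks of 4. At 85/8/7 the seven-patient site is split more unevenly than 2:1 in about 44% of trials.

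**Analysis with a site term.** Information relative to perfect balance is Σ(n_1k·n_0k/n_k)/25, where n_1k and n_0k are the two arms at site k. Its expectation is [25 − Σ(N − n_k)/(4(N − 1))]/25. With three sites Σ(N − n_k) = 200, so this is (25 − 200/396)/25 = 0.980 for any site sizes: an average loss of 2%. The simulated 5th percentile is about 94%. With site-specific lists the efficiency is about 0.996 to 0.999.

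The planned mixed model was simulated with 88 evaluable patients, blocks of 4, a true effect of 0.7 within-site SD, and between-site SD of 0.5 or 1.0 within-site SD. Power is 0.88 to 0.90 with one schedule and 0.88 to 0.91 with stratified lists. Type I error with one schedule is 0.04 to 0.054. Random-site and fixed-site models give almost the same results.

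**Analysis without a site term.** Variance inflation against exact within-site balance is [ICC/(1 − ICC)] × (Σd_k²/2500)/0.04, where 0.04 = 1/50 + 1/50. Average Σd_k²/2500 is 67.3/2500 = 0.0269 at equal sites and 26.9/2500 = 0.0108 at 85/8/7.

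| ICC | ICC/(1 − ICC) ÷ 0.04 | Equal sites | 85/8/7 |
|---|---|---|---|
| 5% | 1.316 | 3.5% | 1.4% |
| 10% | 2.778 | 7.5% | 3.0% |
| 20% | 6.25 | 16.8% | 6.7% |

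In the worst 5% of trials at equal sites the inflation is about 10%, 22% and 48%.

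The mean bias of the unadjusted difference is about 0 in every scenario, and the unadjusted t-test under one schedule keeps its type I error (about 0.04 to 0.05). Its power is 0.85 to 0.86 at between-site SD 0.5 (ICC 0.25/1.25 = 20%) and 0.73 to 0.82 at between-site SD 1.0 (ICC 50%). Part of that shortfall arises because the effect was fixed at 0.7 within-site SD, so a test that ignores site faces a larger total SD.

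**The case against.** The strongest reply is that the plan has already dealt with site where it matters most. Allocation is central and random, the primary model in Statistical Methods includes site, and the remaining loss is about 2%. The larger inflation figures belong to analyses without a site term and rest on assumed ICCs. For the primary endpoint they apply only if the synopsis t-test governs, which is a separate inconsistency. The Fisher tests concern additional endpoints with no power target. All of this stands, and it is why the point is minor.

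A second reply is that stratified allocation alone does little for an unadjusted test. This also stands. With stratified lists the unadjusted t-test becomes conservative (type I error 0.016 to 0.040), and its power rises by at most about 4 points. The site term does most of the work; stratification complements it.

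A third reply is that lists within a site are easier to guess, and the plan gives limiting selection bias as its reason for a single schedule. The cost is real but small when lists are held centrally and block sizes vary.

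A reader might infer three stronger things that the documents do not support.
- That site or surgeon is confounded with device: any imbalance is by chance and averages to zero. The documents do not say how many surgeons operate at each site, and stratifying by site would not by itself balance them.
- That a random effect with three sites corrects only partly: the simulation shows it performing like a fixed site effect.
- That the cap of 85 makes matters worse: small sites are often lopsided but carry little weight, and overall inflation at 85/8/7 is less than half that at equal sites.

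**Conclusion.** The point holds as a minor loss of precision. One schedule with no stated stratification permits chance device imbalance within a site, although site is in the primary model. Under that model the cost is about 2% efficiency on average and at most about 2 points of power. Without a site term, average variance inflation is about 4%, 7% and 17% at equal sites, and about 1%, 3% and 7% at 85/8/7, for ICCs of 5%, 10% and 20%. Validity is not threatened. The 2% average does not depend on block size or site sizes, but it does assume random arrival. The unadjusted figures depend on the assumed ICC and site sizes, for which the documents give no values.

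**What to change.** In Control of Systematic Error/Bias, replace the single schedule with one permuted-block list per site, generated and held centrally by the statistician, concealed from the sites, with randomly varying block sizes (for example 4 and 6). In the synopsis, replace the t-test with the mixed model from Statistical Methods, so that one primary analysis is named and it keeps the site term.

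The cost is three computer-generated lists in place of one, through the same central process, with no change in sample size. It must be done before enrolment starts. There are two small downsides. The next allocation within a site becomes slightly easier to guess, which varying block sizes and central concealment limit. Unfinished blocks can also leave a small remainder: with blocks of 6, an eight-patient site ends 5:3 in about 41% of trials, and the overall split may miss 50:50 by a few patients. The effect on efficiency is negligible.
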